#### **4.8 Consent to Treatment**

Once a patient meets eligibility, a formal consent conference will be undertaken by one of the means listed below.

##### 4.8.1 In-person consent:

- Research staff sign their portion of the consent and the consent form is given to clinical staff who deliver the consent to the patient as part of their clinical duties.
- Research staff will contact the subject or legally authorized representatives (LAR) by telephone or videophone (method dictated by institutional policy) to have the informed consent conversation. *This step confirms subject/LAR identity.*
- If the subject or LAR consents:
  - Subject or LAR signs the consent form and this signature is witnessed by two individuals who document the signing of the consent on a paper attestation form outside the room.
  - OR
  - A picture of the signed consent is made, and emailed to the study staff.
- The subject/LAR retains the consent form, and the signed attestation of consent or copy of the photograph is stored in the research staff records. No copy of the consent is stored due to the potential for transmission of COVID19 virus

##### 4.8.2 Electronic Consenting

- Research staff email the consent to the patient or LAR. If the patient or LAR is offsite, a scan of the consent form can be emailed, faxed, or otherwise electronically transferred to the LAR (method dictated by institutional policy)
- Research staff will contact the subject or LAR by telephone or videophone (method dictated by institutional policy) to have the informed consent conversation. *This step confirms subject/LAR identity.*
  - If the subject or LAR consents a REDCAP survey link can be sent to their personal device and the e-consent RedCap signature process is completed and sent to study-specific RedCap storage where the PI will co-sign the form. This form also indicates the name of the study team member that was involved in the consent process.
  - If using a study-provided device, the subject reads the consent and follows the prompts in RedCap and the signed consent is electronically transmitted to the study-specific RedCap storage where the PI will co-sign the form. This form also indicates the name of the study team member that was involved in the consent process. The device is then disinfected according to local institutional practices.
- The subject/LAR receives an electronic copy of the consent form to the email provided, and the e-signed consent is stored in RedCap the research staff records.

#### 4.8.3 Verbal consent

Because of the nature of this viral disease and the possibility of transmission through direct contact with the subject, verbal consent may also be given by the subject if witnessed and confirmed by two study staff. The verbal consent will be documented on the consent form and signed by the two witnesses.

If the subject cannot read or sign the documents, oral presentation may be made or signature given by the subject's legally appointed representative, if witnessed by two people and documenting that the patient could not read or sign the documents. No patient can enter the study before his/her informed consent has been obtained. The informed consent form is considered to be part of the protocol, and must be submitted by the investigator with the protocol at the time of IRB review.

#### 4.9 Patient Registration to Treatment

To register a patient, the following information should be reviewed by the clinical research nurse (CRN) / clinical research associate (CRA) with the study physician per MCC SOPs to confirm eligibility:

- Copy of COVID19 testing results
- Mobile EKG tracing (outpatients) or standard EKG (inpatients) within 5 days of registration to assess QTc interval
- Eligibility labs, as well as correlative labs to be drawn
- Eligibility Checklist

Once eligibility is confirmed, the CRN/CRA will complete subject registration in the OnCore database (minimum data footprint) for randomization and complete study-required RedCap data forms. To complete the registration process, the CRN/CRA will:

- assign a patient study number
- register the patient on the study in OnCore
- receive the automated treatment arm assignment
- send an email or other communication to the study team of arm assignments.

If a patient is deemed ineligible for treatment their specimens will be retained in the COVID19 BIOBANK if the subject has indicated agreement to specimen collection and long-term storage in the consent form.

At the Day 1 visit or inpatient the following will be completed

- 1) Sign **treatment informed consent** (unless previously e-consented as above)
- 2) Undergo blood testing for eligibility (in subjects who have not had assessment of screening labs within the last 30 days will require blood draw)
- 3) Complete an eligibility questionnaire (age, concurrent diseases, current medications, contact information)
- 4) Undergo a mobile EKG or standard EKG tracing to assess QTc interval (within 5 days of registration)
- 5) Distribute medications, pill diary, and instructions
- 6) Baseline correlative blood sample
- 7) Sputum sample, with OP swab (alternative, if no sputum available)
- 8) Saliva sample
- 9) COVID-19 ordinal scale assessment (See Appendix B)
- 10) Limited visual physical exam unless a more complete exam is clinically indicated.

Day 3 or 4 phone call to assess clinical status and elicit concerns or questions.

Day 7 telehealth (+/- 4 days) is required for all patients to assess toxicity. If a subject has a standard of care telehealth visit during this period, this is also an acceptable toxicity assessment.

Day 10 or 11 phone call to assess clinical status and elicit concerns or questions

Day 14 (+/- 4 days) visit will also be completed in clinic or inpatient hospital.

- 1) Undergo blood testing for toxicity
- 2) Collection of medications, pill diary and instructions
- 3) Mobile EKG tracing (outpatients) or standard EKG (inpatients) to assess QTc interval
- 4) Correlative blood sample
- 5) Sputum sample, with OP swab (alternative, if no sputum available)
- 6) Saliva sample (optional)
- 7) Nasopharyngeal swab (optional and if indicated for standard of care)\*
- 8) COVID-19 ordinal scale assessment (See Appendix B)
- 9) Toxicity assessment via telehealth or phone call (+/-4 days)

Day 28 (+/- 4 days) visit will also be completed in clinic or inpatient hospital.

- 1) Correlative blood sample
- 2) Sputum sample, with OP swab (alternative, if no sputum available)
- 3) Saliva sample (optional)
- 4) Nasopharyngeal swab (optional and if indicated for standard of care)\*
- 5) Serology testing\*
- 6) COVID-19 ordinal scale assessment (See Appendix B)
- 7) Toxicity assessment via telehealth or phone call (+/-4 days)

Day 40 (+/- 4 days) visit. If serology testing is negative or viral load remains positive, patients will be requested to return for a Day 40 visit (optional) will also be completed via drive through (preferred), clinic or inpatient hospital.

- 1) Correlative blood sample
- 2) Sputum sample, with OP swab (alternative, if no sputum available)
- 3) Saliva sample (optional)
- 4) Nasopharyngeal swab (optional and if indicated for standard of care)\*
- 5) Serology testing (optional and if indicated for standard of care)\*
- 6) COVID-19 ordinal scale assessment (See Appendix B)

\*These are considered standard of care tests

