## 9. STATISTICAL CONSIDERATIONS

### 9.1 Study Design/Endpoints

This study is a randomized, multi-arm phase II trial. No proven effective therapies currently exist for COVID19 (Sanders J et al. JAMA April 13, 2020), thus a selection design using the frequentist pick-the-winner design will be employed as early screening for promising therapies. The primary objective is to rapidly evaluate multiple potential inhibitors of SARS-CoV-2 viral replication in COVID19 positive patients with high-risk factors in order to decrease clinical deterioration, defined as a less than 2 point decrease in initial COVID 7-POINT ORDINAL OUTCOMES SCALE within 14 days from study entry (primary). As an example, if a person enters the study at ORDINAL SCALE 6 and does not worsen to 4 or less, that is considered a success.

For each arm a phase I lead in portion, six patients per group will be followed in order to evaluate dose limiting toxicities and preliminary safety. If 2 of the first 5 patients or if  $\geq 2$  of 6 patients experience DLT, the regimen will not be considered safe for further evaluation.

The trial will be powered based on the primary endpoint of the rate of patients who will exhibit less than 2 levels of decrease in COVID 7-POINT ORDINAL SCALE from baseline to Day 14. The goal of selection designs is to select with high probability should a superior treatment exist. Note that hypothesis testing or comparisons between arms or with a placebo is not performed with this design and subsequent trials are needed for definitive hypothesis testing of the promising arm.

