**COVID 7-point ordinal outcomes scale:**

1. Death
2. Hospitalized on invasive mechanical ventilation or ECMO
3. Hospitalized on non-invasive ventilation or high flow nasal cannula
4. Hospitalized on supplemental oxygen
5. Hospitalized not on supplemental oxygen
6. Not hospitalized with limitation in activity (continued symptoms)
7. Not hospitalized without limitation in activity (no symptoms)

*IMP: Artemisia annua, Artesunate, Camostat mesilate, Ivermectin,  
Study #: MCC-20-COVID-01-PMC  
Amendment 4 August 28, 2020*

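### The plan does not require the baseline ordinal score to be fixed before the arm is released, defines baseline in two ways, and lets a one-level baseline call change the primary outcome

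*Combined protocol and SAP*

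**What the plan says.** Section 4.9 names what is reviewed to confirm eligibility before registration: the COVID-19 test result, the EKG, labs and the eligibility checklist. The ordinal score is not there. During registration, staff "receive the automated treatment arm assignment" and then "send an email or other communication to the study team of arm assignments". The Day 1 list follows. Medication is distributed at item 5, and item 9 is "COVID-19 ordinal scale assessment (See Appendix B".

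Section 9.4 blinds staff to the randomization lists only. No section describes a blinded assessor of the score.

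Sections 1.1 and 9.1 measure the fall from the initial score within 14 days of study entry. Section 12.1 instead takes the change from the time of diagnosis, and section 3.1.2 allows a positive test up to 7 days before consent. The section 11 calendar has no line for the scale.

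Section 9.1 illustrates the rule: "if a person enters the study at ORDINAL SCALE 6 and does not worsen to 4 or less, that is considered a success". The Appendix B levels that matter here are:

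- 7: "Not hospitalized without limitation in activity (no symptoms"
- 6: "Not hospitalized with limitation in activity (continued symptoms"
- 5: "Hospitalized not on supplemental oxygen"
- 4: "Hospitalized on supplemental oxygen"

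**The concern.** The baseline score is half of a change endpoint. In an open-label trial, a baseline recorded by someone who already knows the arm is open to unconscious leaning. Here the direction is simple: a lower baseline makes a 2-level fall harder to reach, so it raises the success rate without any clinical difference.

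The stakes are higher because section 9.1 rules out testing between arms or against placebo. Selection rests on the observed success rates, and the interim rules in section 9.6 read the same rate against fixed values of 80% and 90%. A shift in one arm distorts the ranking. A shift common to all arms leaves the ranking largely alone but distorts the fixed-rate readings.

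**Working it through.** **1. Which outcomes depend on the baseline call.** Success means baseline minus later score is less than 2.

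| Later score | From 7 | From 6 | From 5 | From 4 |
|---|---|---|---|---|
| 5 | fall 2, failure | fall 1, success | success | success |
| 4 | failure | failure | success | success |
| 3 | failure | failure | fall 2, failure | fall 1, success |
| 2 or 1 | failure | failure | failure | failure |

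For 7 versus 6, only a later 5 changes the result. For 5 versus 4, only a later 3 does. The 6 versus 5 boundary is hospital admission, which the stratification factor in section 9.4 records at enrollment.

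**2. Reproducing the plan's selection probabilities.** Inputs from section 9.3: n = 60 per arm, four arms, null rate .80, target .90. The probability that arm i is the sole leader is

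P(i) = Σ over k = 1…60 of b(k; 60, p_i) × Π over j ≠ i of B(k−1; 60, p_j),

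where b is the binomial probability and B its cumulative form.

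- Scenario A: .822 for the better arm and .035 for each other arm, as stated.
- Scenario B: .949, as stated.
- Scenario C: .696, against .700 stated.
- Scenario D: .421, as stated.

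Breaking ties at random would give .855 in Scenario A, so the plan counts sole leaders only.

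**3. Size of a shift (assumed).** The documents give no distribution of baseline scores. Suppose 3–10% of patients reach the one later level that matters, and the baseline call is discretionary in half of them.

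- If every such call goes low in one arm and none does elsewhere, the difference is 3% × 0.5 = 1.5 points to 10% × 0.5 = 5 points.
- If calls in the other arms split evenly, the difference halves to 0.75–2.5 points.

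**4. Effect on selection.** Three arms at .80, one at .80 plus the shift, all truly inert:

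| Shift (points) | Shifted arm is sole leader |
|---|---|
| 0 | .21 |
| 0.75 | .24 |
| 1.5 | .28 |
| 2.5 | .34 |
| 5 (extreme) | .50 |

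In Scenario A, shifting one null arm lowers the chance of selecting the truly better arm from .822 to .797 (1.5 points) or .696 (5 points). At the first interim look, the chance that an arm with a true rate of .80 meets the futility boundary of 7 or fewer successes in 10 is .322. A 5-point shift lowers it to .180.

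**The case against.** The Day 1 list is not a strict sequence. It also holds consent, eligibility bloods, the eligibility questionnaire and the EKG, which belong before assignment. Outpatient Arm E product is shipped by the distributor (section 8.1.5), not handed out at item 5. A reader might infer from the numbering that the baseline is always scored with the arm known. The text does not establish that; it only fails to prevent it. This part of the objection stands.

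The 5 versus 4 call rests on oxygen use, which is charted and fairly objective, so it should not be treated as largely discretionary. This also stands. For 7 versus 6, the symptom glosses in Appendix B lean a symptomatic outpatient towards 6, so it would be too strong to say that such a patient fits neither level. The ambiguity is narrower: level 6 couples limitation with symptoms, and a patient who has symptoms but no limitation is not cleanly placed.

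The 5-point figure needs every discretionary call to go one way in one arm only. All four arms are active, and nothing in the documents says that one would be favoured. Confusion caused by the wording alone should be similar across randomized arms. If the endpoint is read at Day 14 itself, patients admitted at level 5 and discharged by then would not change category. Section 9.6 also bases decisions to drop an arm on more than this rate. These points limit the size; they do not remove the gap.

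**Conclusion.** The concern holds as a gap in protection. Nothing in the protocol requires the baseline score to be recorded before assignment or by someone unaware of the arm, the listed order points the other way, and the baseline definitions conflict. The result in step 1 is exact and needs no assumption. The selection figures are illustrative. They rest on assumed shares and on a shift in one arm relative to three others at .80. A reader might infer that the trial's ranking will be biased by a known amount; the documents support neither the presence nor the size of such a bias. The point is a cheap improvement, aimed mainly at the 7 versus 6 call.

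**What to change.** 1. In section 4.9, move the ordinal score to the items completed before registration, and lock it before OnCore releases the assignment.
2. In sections 1.1, 9.1 and 12.1, state that this pre-assignment score is the baseline, replacing the reference to diagnosis in 12.1.
3. Add a row for the scale to the section 11 calendar.
4. In Appendix B, make levels 6 and 7 mutually exclusive on one stated criterion. For example, level 7 could require no COVID-19 symptoms and no new limitation in activity, with level 6 if either is present.

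The cost is one reordered item, one form lock and short text edits, with no added visit or sample size. There are downsides. The pre-registration step becomes slightly longer. Outpatients who e-consent before coming to clinic (section 4.7.3) may need remote scoring. Because section 4.10 allows treatment to start within 7 days of registration, the baseline may precede the first dose by up to 7 days.

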#### 4.10 General Guidelines

Following registration, patients should begin protocol treatment within 7 days. Issues that would cause treatment delays should be discussed with the Principal Investigator. If a patient does not receive protocol therapy following registration, the PI and the statistician must be consulted as soon as possible.

## 5. BIOMARKER, CORRELATIVE, AND SPECIAL STUDIES

### 5.1 Summary Table for Specimen Collection

Time Point	Specimen	Send Specimens To:
Archival		
	
 
• Discarded tissue or blood samples from original COVID19 testing
 
• Residuals from any of the research samples collected below
 
	Center for Clinical and Translational Science (CCTS) COVID-19 Research Registry and Specimen Bank (CRRSB)
Baseline – Day 1		
	
 
• 10 mL and 6 mL blood in EDTA (purple top) tubes for antibody testing, procalcitonin, CRP and cytokines
 
• 5 mL blood in ACD (yellow top) tube for platelet function assays (optional)
 
• 8mL blood in CPT tube (optional)
 
	Biospecimen Procurement and Translational Pathology Shared Resource Facility (BPTP SRF) or CCTS CRRSB

	
 
• Sputum sample (Mandatory) or OP swab (alternative, if sputum is unavailable)
 
• 1 ml of saliva (optional)
 
	
Day 14 (+/- 4 day)		
	
 
• 10 mL and 6 mL blood in EDTA (purple top) tubes for antibody testing, procalcitonin, CRP and cytokines
 
• 5 mL blood in ACD (yellow top) tube for platelet function assays (optional)
 
• 8mL blood in CPT tube (optional)
 
• Sputum sample (Mandatory) or OP swab (alternative, if sputum is unavailable)
 
• 1 ml of saliva (optional)
 
	BPTP SRF or CCTS CRRSB
Day 28(+/- 4 days)		
	
 
• 10 mL and 6 mL blood in EDTA (purple top) tubes for antibody testing, procalcitonin, CRP and cytokines
 
• 5 mL blood in ACD (yellow top) tube for platelet function assays (optional)
 
• 8mL blood in CPT tube (optional)
 
• Sputum sample (Mandatory) or OP swab (alternative, if sputum is unavailable)
 
• 1 ml of saliva (optional)
 
	BPTP SRF or CCTS CRRSB
Day 40(+/- 4 days)		
	
 
• 10 mL and 6 mL blood in EDTA (purple top) tubes for antibody testing, procalcitonin, CRP and cytokines
 
• 5 mL blood in ACD (yellow top) tube for platelet function assays (optional)
 
• 8mL blood in CPT tube (optional)
 
• Sputum sample (Mandatory) or OP swab (alternative, if sputum is unavailable)
 
• 1 ml of saliva (optional)
 
	BPTP SRF or CCTS CRRSB

## 5.2 Specimen Procurement Kits and Scheduling

### 5.2.1 Specimen Procurement Kits

Specimen procurement kits will be supplied by the Biospecimen Procurement and Translational Pathology Shared Resource Facility (BPTP SRF).

## 5.3 Specimen Collection and Processing

**Residual Clinical Samples** (blood, sputum, saliva, nasopharyngeal and oropharyngeal swab)

[figure not shown]
samples): Residual clinical samples will include serum and plasma originally collected in EDTA, citrated or heparinized tubes and subsequently stored at -20°C in 5ml pour-off tubes. Subsequently, these samples will be transferred to the Markey Cancer Center Biospecimen Procurement and Translational Pathology Shared Resource Facility (BPTP) or the Center for Clinical and Translational Science (CCTS) COVID-19 Research Registry and Specimen Bank. BPTP or CCTS staff will log, and label and store the residual clinical plasma and serum specimens at -80°C or lower. Upper respiratory tract samples will include residual nasopharyngeal and oropharyngeal swab specimens stored in viral transport media (VTM) and initially frozen at -70°C. After transport to the BPTP, the staff will log, label and store the specimens at -80°C or lower.

**Research Peripheral Blood Samples for Procalcitonin, D-Dimer, Cytokines, Seroconversion, and Platelet Function:** One 10-mL and one 6-mL EDTA (purple top) tubes, one 5 mL blood in ACD (yellow top) tube and one 8mL blood in CPT tube (optional) of blood will be drawn and immediately delivered to the Markey BPTP-SRF lab or the CCTS COVID-19 Research Registry and Specimen Bank. EDTA and CPT tubes will be processed as soon as possible, but at most will occur within 24 hours of blood draw. ACD tubes will be delivered immediately to the [name] lab (see below). Biobank staff will freeze a 1-mL aliquot of whole blood, then centrifuge the remainder at ~1,200 RCF for 12 minutes to separate and collect plasma and buffy coat. Samples will be logged and labeled and aliquoted and stored frozen at -80°C or lower. Delivery and receipt of refrigerated blood samples will occur Monday through Friday.

**Research Oropharyngeal (OP), for Viral Load:** One swab sample will be collected per patient following standard procedure at each study time point, immediately placed in viral transport media and refrigerated or stored at -80°C or lower. Deliveries and receipt of frozen or refrigerated samples will occur Monday through Friday.

**Research Sputum Samples for Viral Load:** One sputum sample per patient at each study time point will be collected following standard protocol. The specimens will be delivered immediately to the BPTP lab. Samples will be logged and labeled and stored at -80°C or lower.

**Research Saliva Samples:** One optional saliva sample per patient at each study time point will be collected following standard protocol. The specimens will be collected in a standardized kit and held at 4°C until delivery to the BPTP lab. Samples will be logged and labeled and delivered to the [name] Lab.

Research specimen processing and delivery algorithm

#### 5.4 Shipping/Dispensing of Specimens

Samples will be transported to the MCC BPTP SRF or the CCTS COVID-19 Research Registry and Specimen Bank for processing and transport to the appropriate labs as above.

### 6. TREATMENT PLAN

Subjects will be approached at the time of initial COVID-19 testing or within 7 days of a positive test. Prior to any study-required tests, subjects must first provide written informed consent to participate in this study.

#### 6.1 Agent Administration

The CURE Alliance Drug Steering Committee will serve as the drug selection committee to identify the appropriate new drugs for each new arm of this clinical trial. Treatment will be administered on an outpatient or inpatient basis provided that entry criteria are met. If emerging data indicates futility of a medication in one or more arms of our study, and was tested in a similar patient population in a randomized clinical trial or trials, the study drug selection committee may recommend removal of that drug treatment arm for futility with approval of the study team. Once a futility endpoint is met in an arm, we will replace that arm with the next appropriate proposed arm with approval of the CURE Alliance Drug Steering Committee. **All subjects receive standard supportive treatment throughout their infection, whether outpatient or during inpatient hospitalization.** Reported adverse events and potential risks are described in Section 10.

Treatment regimens will be evaluated and novel agents selected by the steering committee. Should drug supply become unavailable that arm would pause until drug supply is available.

Regimen Description- Arm C				
Agent	Formulation Strength	Daily Dose	Route	Schedule
Ivermectin	3 mg tablet	12-15 mg	Oral	Weight < 75kg: 4 tabs on Days 1 and 2, (12 mg total daily dose) Weight ≥ 75kg: 5 tabs on Days 1 and 2, (15 mg total daily dose)

Regimen Description- Arm D				
Agent	Formulation Strength	Daily Dose	Route	Schedule
Camostat Mesilate	100 mg tablet	600mg	Oral	2 tab TID after a meal (600 mg total daily dose) Days 1-14

Regimen Description- Arm E				
Agent	Formulation Strength	Daily Dose	Route	Schedule
Artemisia annua tea or coffee	Decaf coffee 450mg per pod Tea 225mg per bag	1350 mg	Oral	One 8oz brewed tea (two bags) or one coffee pod TID Days 1-14

Regimen Description- Arm F				
Agent	Formulation Strength	Daily Dose	Route	Schedule
Artesunate	100mg	200mg	Oral	Two tabs once day (200mg total) Days 1-14

Patients will be assigned to a treatment arm according to the randomization process described in Section 9 of this protocol

Since there are no safety data for the medications to be evaluated on all arms of this study in the mild to moderate SARS-CoV-2 infected population, the first six patients on each arm will be evaluated for any grade 3 or higher hematologic or non-hematologic toxicity for 14 days. Patients coming off study before the first 14 days for reasons other than toxicity will be replaced. If two or more of the six patients in this arm of the study develop unacceptable toxicity, the treatment for that arm would be considered unsafe and stopped. Patients exhibiting rapid progression of COVID-19 symptomatology requiring intensive care hospitalization or intubation will come off study and will be considered failures in terms as per the primary endpoints of the study but nor for safety and will be replaced if these cases occurred during the phase 1 portion of the study.

Once the phase 1 portion safety run-in has concluded, that arm will be opened for phase II accrual.

Patients will be assigned to each arm in cohorts of three at a time until accrual numbers for each arm are fulfilled or discontinued due to safety concerns occurring beyond the Phase 1 portion. Monthly phone conferences among investigators during enrollment will take place.

Patients will undergo baseline mobile EKG or standard EKG to evaluate QTc interval on Day 1 (or within 5 days of registration if inpatient) and a repeat EKG at Day 14 (+/-4 days). Any Chest X-ray or CT scan of the chest that is performed for routine care will be reviewed by the PI for eligibility and recorded on case report forms. NOTE: if a patient develops a myocardial infarction or grade 3 or 4 cardiac arrhythmia while on the 14 days of drug, they should be immediately taken off study medication and receive standard of care treatment per their treating physician.

Patients will be followed for clinical outcomes by phone contact each week and hospitalizations, and all complications will be recorded on adverse event case report forms.

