## **6.3 Duration of Therapy**

In the absence of treatment delays due to adverse event(s), treatment is given until one of the following criteria applies:

- Intercurrent illness that prevents further administration of treatment
- Unacceptable adverse event(s)
- Patient decides to withdraw from the study
- General or specific changes in the patient's condition render the patient unacceptable for further treatment in the judgment of the investigator
- Patient non-compliance
- Pregnancy
- The drug manufacturer can no longer provide the study agent
- Admission to the Intensive Care Unit and/or need for mechanical ventilation. At this

time, the treating physician will have the ability to continue study drug, discontinue therapy, place the patient on another study trial, or treat the patient with alternative therapies, per their clinical judgement. At this point, the patient will be followed by the study team to track outcomes and monitor for adverse events that might be attributable to study drug but the drug will be considered to have failed the primary endpoint

The reason(s) for protocol therapy discontinuation, the reason(s) for study removal, and the corresponding dates must be documented in the Case Report Form (CRF). For clarity, “off treatment” is the date when all medication has been completed (including the normal observation period) or discontinued due to one of the factors above, and no further treatment is planned. This is the date the patient has been officially taken off treatment. “Off study” is the date after which no further follow-up of the patient will occur

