### **10.1 Evaluation of Toxicity**

All patients will be evaluable for toxicity from the time of their first treatment with the investigational agents described above.

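### The run-in replacement rule turns on coming off study, so early drug-stoppers who stay in follow-up can fill safety slots and the 2-of-6 gate can clear an arm on fewer than six adequately exposed patients

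*Combined protocol and SAP*

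**What the plan says.** Section 6.1 puts a safety run-in at the start of every arm: "the first six patients on each arm will be evaluated for any grade 3 or higher hematologic or non-hematologic toxicity for 14 days". The arm is treated as unsafe and stopped under this condition: "If two or more of the six patients in this arm of the study develop unacceptable toxicity". Zero or one therefore opens it to phase II. Section 9.1 restates the design ("six patients per group will be followed in order to evaluate dose limiting toxicities and preliminary safety"). Its wording, 2 of the first 5 or at least 2 of 6, is the same rule with an earlier stop.

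Section 6.1 replaces a run-in patient in two situations:
- "Patients coming off study before the first 14 days for reasons other than toxicity will be replaced".
- A patient whose COVID-19 progresses rapidly to intensive care or intubation "will be replaced if these cases occurred during the phase 1 portion of the study".

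Section 6.3 distinguishes two end dates. Off treatment "is the date when all medication has been completed (including the normal observation period) or discontinued due to one of the factors above". Off study "is the date after which no further follow-up of the patient will occur". The reasons it lists for ending treatment include intercurrent illness, non-compliance and investigator judgement. Section 6.4 follows patients for up to 40 days from the start of therapy or until death and makes no exception for those who stop drug.

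Section 6.2 limits DLTs to the first 14 days of study treatment, which is a time window and not a minimum exposure. Neither 6.1, 6.2 nor 9.1 sets a minimum number of doses. The only general statement on evaluability is in Section 10.1: "All patients will be evaluable for toxicity from the time of their first treatment".

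**The concern.** Replacement depends on the end of follow-up, while the information in a run-in slot depends on drug taken. A patient in a 14-day regimen who stops after a dose or two through non-compliance, and is still followed to Day 14, meets neither replacement condition. With no related grade 3 or higher event, that patient is one of the six and DLT-free.

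The same happens to a patient who stops early because of a toxicity below grade 3. The reason is toxicity, so 6.1 does not replace the patient, and the event is not a DLT.

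On the working assumption that less drug does not raise the DLT risk, the error runs one way: under-exposure lowers the expected DLT count and makes clearance more likely. Section 6.1 justifies the run-in by the absence of safety data for these medications in this population, and the run-in is the prespecified gate to the rest of the arm's planned 60 patients.

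**Working it through.** **Reading the rule.** Take a patient in Arm D who takes one dose, stops for non-compliance and attends Day 14.
1. Off treatment under 6.3: yes, drug is discontinued.
2. Off study under 6.3: no, follow-up continues (6.4).
3. First replacement condition in 6.1: not met, because it requires coming off study.
4. Second replacement condition: not met, because there was no intensive care or intubation.
5. Minimum exposure: none stated.

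The patient stays among the six and, without a DLT, counts as safe.

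**Exposure by arm (6.1).** One dose is 1 of 2 daily doses in Arm C, 1 of 3 × 14 = 42 in Arms D and E, and 1 of 14 in Arm F. The gap therefore concerns mainly D, E and F.

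**Chance of clearing an arm.** The plan gives no operating characteristics for the 2-of-6 rule, so there is no figure to reproduce. The true DLT risk p is not in the documents either; 0.10 to 0.40 is an assumed range.

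With n fully exposed patients and the other slots at negligible risk:

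P(clear) = (1 − p)^n + n·p·(1 − p)^(n−1)

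At p = 1/3:
- n = 6: 64/729 + 192/729 = 256/729 = .351
- n = 5: 32/243 + 80/243 = 112/243 = .461
- n = 4: 16/81 + 32/81 = 48/81 = .593

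| Assumed p | Six exposed | One slot unexposed | Two slots unexposed |
|---|---|---|---|
| 0.10 | .886 | .919 | .948 |
| 0.20 | .655 | .737 | .819 |
| 1/3 | .351 | .461 | .593 |
| 0.40 | .233 | .337 | .475 |

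**If the early stopper keeps half the risk.** With five fully exposed patients and one at risk p/2:

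P(clear) = (1 − p)^5 + 5p(1 − p)^4 × (1 − p/2)

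- p = 0.10: .59049 + .32805 × .95 = .902
- p = 0.20: .32768 + .40960 × .90 = .696
- p = 1/3: .13169 + .32922 × .8333 = .406
- p = 0.40: .07776 + .25920 × .80 = .285

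With two such patients at p = 1/3 the figure is .466.

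**How often a slot might be affected.** The documents give no early-stop rate. If each patient independently had an assumed 10% or 20% chance of stopping early while staying in follow-up, the chance of at least one affected slot in six would be 1 − .9^6 = .47 or 1 − .8^6 = .74.

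**The case against.** The best counter-argument is that 6.1 does not itself keep to the 6.3 definition. It says patients who progress to intensive care or intubation come off study, while 6.3 says the study team goes on following them. On that looser usage, the replacement sentence may have been meant to cover anyone who stops drug before Day 14 for a non-toxicity reason. This stands as a statement about possible intent. A reader might infer that the plan deliberately counts one-dose patients as safe; the documents do not support that. They support a narrower statement: the only definition given leads to that count, and the two sections conflict.

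Three further points limit the concern.
- Section 6.3 states continued follow-up explicitly only for intensive care or ventilated patients. For other drug-stoppers it follows from 6.4.
- Section 10.1 concerns toxicity evaluability in general. It does not define who counts among the six, and should not be read as doing so.
- The size depends on the assumed risk. Section 8.1 lists no toxicity above 10% for ivermectin, camostat or *Artemisia annua*, though it lists neutropenia, anemia and nausea for artesunate. A DLT must also be grade 3 or higher and at least possibly related (6.2). Low DLT risks are therefore plausible, and there the effect is small.

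Other safeguards exist. Section 6.1 allows an arm to be discontinued for later safety concerns, 10.3 requires expedited reporting of drug-related events of any grade during the run-in, 9.6 brings safety into decisions on dropping an arm, and 13.3 lets the monitoring committee suspend or terminate the trial. It would be wrong to infer that an unsafe arm would run unchecked to 60 patients. These safeguards lessen the consequence, but they do not repair a gate passed on too little exposure.

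**Conclusion.** The concern holds for the rule as written, mainly in Arms D, E and F. The exact claim is fewer than six adequately exposed patients; a one-dose patient is exposed, and in Arm C one dose is half the planned regimen, so a claim of unexposed patients across all arms would go too far.

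One effectively unexposed slot adds about 3 points to the chance of clearing an arm at an assumed DLT risk of 0.10, 8 points at 0.20, and 10 to 11 points at 1/3 to 0.40. With half the risk retained, the increase is about 2 points at 0.10 (.886 to .902) and 5 to 6 points at 1/3 (.351 to .406). All of this rests on assumed DLT risks, and how often early stopping would occur is unknown. The change should be made because the error favours clearance and the correction is cheap.

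**What to change.** Reconcile the use of off study and off treatment between 6.1 and 6.3. Then add an evaluability rule to 6.1 and refer to it in 9.1, for example:

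*A run-in patient is DLT-evaluable if he or she has a DLT at any exposure, or completes 14 days of follow-up and has taken at least a prespecified share of the arm's planned doses, by diary and product count. Patients who are not DLT-evaluable are replaced for the run-in count only and remain in the safety set and the m-ITT population.*

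The sponsor sets the minimum share separately for each arm. The text must also say how a patient who stops early for a toxicity below DLT grade is counted, so that this patient does not fill a slot as DLT-free by default. None of this changes a dose or the 2-of-6 threshold; it changes who is counted.

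The cost is a few sentences. Diaries (Appendix C) and returned medication (4.9, Day 14 visit) are already collected, and compliance is already a secondary objective (1.2.6). The downside is that an affected arm may wait for one or two more run-in patients before it opens. Counting a DLT at any exposure while replacing only DLT-free early stoppers also makes the gate slightly stricter if early stoppers carry real risk, which is the cautious direction for a run-in.
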